9.4. Dose Adjustment Criteria

Local tolerance will be followed very carefully during the study. Subjects will receive information on study drug use and stopping rules and will be instructed to contact the site with any safety/tolerability issues. Study personnel will telephone subjects in between scheduled visits (i.e., at Day 7 and Day 45) to assess safety; an unscheduled clinic visit may be performed, if necessary. During all clinic visits, the investigator will assess local tolerability on a 0-3 scale (0 = none, 1 = mild, 2 = moderate, 3 = severe) for each treated body area (chest/abdomen, back, arms, legs, and face/neck), and the following procedures will be followed:

- If a score of 2 (moderate) is recorded on a local tolerability assessment scale (stinging/burning, pruritus, erythema) on any treated area (e.g., the face), the study drug will be applied on this area only once weekly, until the score returns to <2. Continue to treat all other areas twice weekly provided the score is <2 on those areas.
- If a score of 3 (severe) is recorded on a local tolerability assessment scale (stinging/burning, pruritus, erythema) on any treated area, the study drug will not be applied on that area until the score is back to <3 (i.e., “drug holiday”). Continue to treat all other areas twice weekly provided the score is <2 on those areas.

Any changes in dosing must be documented in the subject diary and the eCRF.

9.4.1 Stopping Rules

A subject's treatment in either the Double-blind Period or the Open-label Extension must be stopped if any of the following occur:

- Subject becomes pregnant or suspects they are pregnant
- Subject has severe (score of 3) local application site AEs that do not abate with “drug holiday” and reintroduction of IP.
- Subject has clinically significant changes in laboratory values (liver function tests, cholesterol/triglycerides – which may occur with systemic retinoid use)

Any changes in dosing must be documented in the subject diary and the eCRF.

9.5. Treatment Compliance

Subjects will be asked to record their twice-weekly applications of IP in the diary during both the Double-blind Period and the OLE. Deviations from the planned doses (missed dose or timing) will be recorded on the subject's eCRF. Study personnel will review diaries at each visit and diaries will be collected as source documents. Information from subject diaries will be transcribed on the appropriate eCRF pages for documentation of subject compliance with the IP.

Study personnel will assess treatment compliance with IP regimens by weighing IP tubes before dispensing and upon return and by questioning the subject, at every postrandomization visit. A participant is compliant with study product if he or she takes at least 80% of the scheduled doses as assessed by diary entries, supplemented by tube weight. A subject who is not compliant (used 80–120% of IP tubes) will be counseled at each visit on the importance of using the IP as instructed.

Subjects who taper to once-weekly application or who take a “drug holiday” for tolerability will not be reported as having deviated from the protocol (see Section 9.4 for dose adjustment and stopping rules); any changes in dosing must be documented in the subject diary and the eCRF.

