13.1.1 Analysis Populations

The following 5 analysis populations are planned for the Double-blind Period of this study:

- Safety: all subjects who are randomized to treatment and receive at least 1 application of study drug in the Double-blind Period. This population will be the primary population for analyses of safety.
- Intent-to-treat (ITT): all randomized subjects. This population will be used as the primary population for the analysis of efficacy for the Double-blind Period of the study.
- Modified intent-to-treat (mITT): all subjects in the safety population with at least 1 postbaseline assessment of efficacy in the Double-blind Period.
- Per-protocol (PP): subjects in the mITT Population who met all inclusion criteria and no exclusion criteria, were compliant with study drug application, and who had no significant protocol deviations.
- Pharmacokinetic: all subjects in the Safety Population who have at least 1 plasma sample with quantifiable concentration. This population will be used to summarize all PK endpoints.

The following analysis populations are planned for the OLE of this study:

- OLE Safety: all subjects who complete the 90-day Double-blind Treatment Period and receive at least 1 application of study drug in the OLE.
- OLE ITT: all subjects who complete the 90-day Double-blind Treatment Period and sign the OLE informed consent.
- OLE mITT: all subjects in the OLE safety population with at least 1 assessment of efficacy after Visit 6.
- OLE PP: all subjects in the OLE mITT population who met all inclusion criteria and no exclusion criteria, were compliant with study drug application from baseline through EOT, and who had no significant protocol deviations throughout the study.

Inclusion in the analysis populations will be determined prior to database lock. Deviations related to COVID-19 will also be evaluated in determining PP population eligibility.

If a subject is randomized incorrectly or is administered the incorrect IP, analyses of the ITT and mITT populations will be based on the assigned treatment whereas all other analyses will be based on the actual treatment received.

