10.1. Study Duration

10.1.1 Overall Study Schedule

The overall study duration is expected to be approximately 19 months.

The planned sequence and maximum duration of the study periods will be as follows:

1. Screening: up to 35 days (after signing informed consent, if necessary, washout may be up to 3 months, and subjects should return to the site after washout to complete the study eligibility requirements).
2. Double-blind treatment: Twice weekly for 12 weeks.
3. Optional Open-label Extension treatment: Twice weekly for 12 weeks.
4. Follow-up: 14 days after last study drug application.

The maximum treatment duration for each subject is approximately 12 weeks for subjects who choose not to continue into the OLE, and 24 weeks for those who choose to continue.

The maximum study duration for each subject is approximately 229 days (33 weeks).

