9.5. Treatment Compliance

Subjects will be asked to record their twice-weekly applications of IP in the diary during both the Double-blind and OLE Periods. Deviations from the planned doses (missed dose or timing) will be recorded on the subject's eCRF. Study personnel will review diaries at each visit and diaries will be collected as source documents. Information from subject diaries will be transcribed on the appropriate eCRF pages for documentation of subject compliance with the IP.

Study personnel will assess treatment compliance with IP regimens by weighing IP tubes before dispensing and upon return and by questioning the subject, at every post-randomization visit. A participant is compliant with study product if he or she takes at least 80% of the scheduled doses as assessed by diary entries, supplemented by tube weight. A subject who is not compliant (i.e.

used $\leq 80\%$ or $\geq 120\%$ of IP tubes) will be counseled at each visit on the importance of using the IP as instructed.

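### Section 9.5 labels use of 80–120% of tubes as non-compliance, the reverse of its own rule that at least 80% of scheduled doses is compliant

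*Protocol*

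**What the plan says.** Protocol Section 9.5 first gives a definition: "A participant is compliant with study product if he or she takes at least 80% of the scheduled doses as assessed by diary entries", with tube weight as a supplement. The next sentence is an instruction to sites: "A subject who is not compliant (used 80–120% of IP tubes) will be counseled at each visit". The same section adds that tapering or a drug holiday for tolerability is not to be logged as a deviation. Section 13.1.3 repeats this.

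The file also holds an earlier protocol text. Its Section 9.5 has the same definition, but its parenthesis reads "used $\leq 80\%$ or $\geq 120\%$ of IP tubes". In the Amendment 2 summary of amended sections, the row for Section 9.5 records only the added taper/holiday sentence.

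Compliance is used again in Section 13.1.1, where PP subjects are those in the mITT population who met the entry criteria, "were compliant with study drug application, and who had no significant protocol deviations". The OLE PP set has a parallel condition.

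The version with the COVID-19 appendix is in the file only from Section 13 onward. The Amendment 2 text of Section 9.5 is therefore the latest that can be read.

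**The concern.** Two adjacent sentences cannot both be applied. The first sets a floor of 80%. The second gives the range around full use as the meaning of non-compliant. Site staff act on the second, because it tells them whom to counsel. Taken at its word, it sends counseling to subjects at or near 100% and omits those at 50% or 130%, for whom counseling is intended.

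The same word, compliant, also decides who is counted in the Section 13.1.3 compliance summary and who enters PP and OLE PP. A term that carries two opposite meanings in its defining section should not be left as a membership condition for an analysis set.

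A smaller gap sits beside this. Section 9.5 does not say whether scheduled doses means the full twice-weekly plan or the plan after a reduction directed under Section 9.4.

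**Working it through.** **Step 1. Compare the two sentences, and the earlier text.** Section 9.2 has one tube per application, so for this comparison I treat percentage of doses and percentage of tubes as the same quantity.

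| Use | At-least-80% rule | Current parenthesis (80–120% = not compliant) | Earlier parenthesis (≤80% or ≥120% = not compliant) |
|---|---|---|---|
| 50% | not compliant | not caught | not compliant |
| 79% | not compliant | not caught | not compliant |
| 80% | compliant | not compliant | not compliant |
| 100% | compliant | not compliant | not caught |
| 120% | compliant | not compliant | not compliant |
| 121% | compliant | not caught | not compliant |

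From 80% to 120% the current parenthesis contradicts the rule. Below 80% it fails to catch anyone the rule fails. Restoring the earlier parenthesis would correct the direction but leave two conflicts: at exactly 80%, and from 120% upward, because the rule has no ceiling. Exactly 80% cannot occur on a count of 24 doses (0.8 × 24 = 19.2), but it can on tube weight or on the doses in a visit interval (for example 8 of 10).

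**Step 2. When could a directed reduction fail the 80% rule?** The schedule is "Double-blind treatment: Twice weekly for 12 weeks" (Section 10.1.1), so 2 × 12 = 24 doses. At least 19.2 are needed, hence 20, and at most 4 may be missed. Suppose scheduled doses means the unreduced plan and every treated area is reduced together:

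- Once-weekly taper, losing 1 dose a week: 4 weeks gives 20/24 = 83.3% (passes); 5 weeks gives 19/24 = 79.2% (fails).
- Holiday, losing 2 doses a week: 2 weeks gives 20/24 = 83.3% (passes); 3 weeks gives 18/24 = 75.0% (fails).
- With 26 doses, counted over 90 days, 21 are needed: taper fails at 6 weeks (20/26 = 76.9%) and holiday at 3 weeks (20/26 = 76.9%).

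**Step 3. What Section 9.4 directs.** Reductions are by area. At a score of 2, "the study drug will be applied on this area only once weekly, until the score returns to <2"; at a score of 3, "the study drug will not be applied on that area until the score is back to <3". In both cases: "Continue to treat all other areas twice weekly provided the score is <2 on those areas". While any area stays on twice weekly, application days continue and the dose count is 24/24 = 100%. If scheduled doses means the plan after reduction, a subject who follows the directed taper or holiday also scores 100%.

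**The case against.** The best defence is that the slip is harmless. The operative definition comes first and is clear, the parenthesis only steers counseling, and any sensible reader will see what was meant. It is also fair that a later Section 9.5, not in the file, may already be corrected, and that the denominator for PP compliance is normally settled in the SAP, which is not shown.

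Most of this stands as a limit on size, but it does not remove the point. The contradiction lies in an instruction that sites follow, and an SAP cannot correct what sites are told to do.

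A reader might go further in either of two directions, and the documents support neither.

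- *That the reversed band flips PP membership.* It does not, as long as PP uses the at-least-80% definition, which is stated correctly.
- *That ordinary tapering for irritation pushes active-arm subjects out of PP and inflates its effect.* It is true that the deviation exemption does not mention the separate compliance condition. But area-specific reduction leaves the dose count at 100% (step 3). Only the amount used falls, and the role of tube weight as a supplement is not defined. No passage gives the share of subjects reduced on all areas or their success rate, so neither the size nor the direction of any bias can be derived. ITT is the primary efficacy population, PP membership is fixed before database lock, and OLE PP has no comparator arm and no inferential efficacy testing.

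**Conclusion.** The parenthesis in Section 9.5 is wrong as written. It contradicts the sentence before it across the whole 80–120% range and misses every subject below 80%. The earlier text and the absence of a log entry suggest an unintended edit, but the finding rests on the two adjacent sentences alone. The consequence is misdirected counseling and an ambiguous compliance term; no primary result is at risk. It should be corrected.

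The undefined denominator is a minor clarification. On the dose count it matters only if all treated areas are reduced together for at least 5 weeks (taper) or 3 weeks (holiday) out of 24 planned doses, and only if scheduled doses means the unreduced plan. It then affects only the secondary PP sets and the descriptive compliance counts.

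This conclusion assumes that the Amendment 2 text of Section 9.5 is still in force.

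**What to change.** Rewrite the two sentences of Section 9.5 so that the non-compliant band is the exact complement of the compliant range, on one stated measure, with no shared value at 80%. The sponsor has to decide whether there is a ceiling. If there is none, non-compliant is below 80%. If 120% is meant as a ceiling, compliant is 80% to 120% inclusive and non-compliant is anything below or above. Point the compliance condition in Section 13.1.1 (PP and OLE PP) and the count in Section 13.1.3 to that same range.

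Add one phrase saying whether scheduled doses is the plan before or after Section 9.4 reductions, and what tube weight contributes when it disagrees with the diary.

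The cost is a few words in Section 9.5, a cross-reference in Section 13.1.1 and a clarification to sites. Section 14.8 requires a formal amendment, so this can go with the next one. No new data are needed, since dosing changes are already recorded in the diary and eCRF, and no dosing or clinical rule is touched.

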9.6. Method of Assigning Subjects to Treatment Groups

In the double-blind, parallel-group, randomized period of the study, subjects who meet study entry criteria will be randomly assigned in a 1:1:1 ratio to trifarotene cream HE1 100 µg/g or 200 µg/g or vehicle cream. The randomization schedule will be computer generated using a permuted block algorithm and will randomly allocate IP to randomization numbers. The randomization numbers will be assigned sequentially through a central interactive web response system (IWRS) as subjects are entered into the study. Study center will not be a blocking factor in the randomization schedule.

Premier Research will prepare the randomization schedule before the start of the study. No one involved in the study performance will have access to the randomization schedule before the official unblinding of treatment assignments. No subject will be randomized into this study more than once.

In the OLE, all subjects will receive trifarotene cream HE1 200 µg/g.

9.7. Blinding and Unblinding Treatment Assignment

All subjects, investigators, and study personnel involved in the conduct of the Double-blind Period of the study, including data management, will be blinded to treatment assignment with the exception of a specified unblinded statistician and programmer from Premier Research who will have access to the randomization code. The statistician will have access to unblinded data if there is an unblinded DSMB review.

Study personnel will make every effort to safeguard the integrity of the study blind to minimize bias in the conduct of the study. Treatment unblinding is discouraged if knowledge of the treatment assignment will not materially change the planned management of a medical emergency. Unblinding will be permitted in a medical emergency that requires immediate knowledge of the subject's treatment assignment.

The investigator may discuss with the medical monitor in advance of unblinding a subject, if possible, if it is not deemed an emergency. However, the investigator has the ultimate decision for unblinding a subject for medical treatment and no procedures will prevent or delay necessary unblinding in an emergency for the subject's safety. For emergency unblinding, study personnel will use the IWRS code. If the investigator is not able to discuss treatment unblinding in advance, then he/she must notify the medical monitor as soon as possible about the unblinding incident without revealing the subject's treatment assignment.

The investigator or designee must record the date and reason for treatment unblinding on the appropriate eCRF for that subject. In all cases that are not emergencies, the investigator must discuss the event with the medical monitor prior to unblinding the subject's treatment assignment.

If treatment assignment is unblinded for an individual subject, study personnel will be notified of that subject's treatment assignment without unblinding the treatment assignments for the remaining subjects in the study. Thus, the overall study blind will not be compromised. If a subject's treatment assignment is unblinded, he/she may or may not be asked to withdraw from the study. The investigator will make this decision after consultation with the medical monitor.

The primary analysis period is the first 12 weeks of treatment (i.e., the Double-blind Period). Overall unblinding will take place at the end of the Double-blind Period of the study only after database lock has been achieved. A second analysis will take place for endpoints assessed from Week 12 through the OLE.

9.8. Permitted and Prohibited Therapies

All concomitant medications used (including over-the-counter medications and herbal supplements) will be recorded in the source document and on the appropriate eCRF.

Upon signing informed consent and entering the Screening Period, subjects will stop using physical and medical treatments for LI, including balneotherapy, and may begin to washout prohibited topical and systemic treatments with designated washout periods ([Table 9-1](#)), as applicable. Washout may be up to 3 months, as necessary.

Table 9-1: Washout Periods for Prohibited Medications

Medication	Washout Period
Topical Treatments	
Corticosteroids (except inhaled and ophthalmic corticoids)	2 weeks
Retinoids (e.g., tretinoin, tazarotene)	4 weeks
Vitamin D analogues	2 weeks
Immunosuppressants (e.g., tacrolimus)	2 weeks
Antracene derivatives, tar and salicylic preparations	2 weeks
Keratolytics (such as urea, lactic acid, propylene glycol, salicylic acid) except keratolytic shampoo	2 weeks
Systemic treatments	
Retinoids	8 weeks
Oral Vitamin A supplementation more than 3500 IU per day	2 weeks
Medication interfering with bone activity, e.g., corticosteroids, thyroid hormones, cytotoxics, bisphosphonates, calcitonins, tetracyclines, quinolones, thiazides, salicylates in long-term course, heparin, theophylline, barbiturates, colchicines (except Vitamin D analogues taken at stable dose since at least 1 month)	8 weeks
QT prolonging drugs	5 half lives
Enzymatic inductors (such as rifampicine, phenytoin, carbamazepine, phenobarbital, St. John's Wort)	3 months
CYP2C9 and 2C8 inhibitors (not all inclusive: gemfibrozil, fluconazole, fluvoxamine, sulfaphenazole, miconazole, amiodarone, sertraline, sulfamethoxazole, valproic acid, voriconazole, trimethoprim, rosiglitazone, pioglitazone)	5 half lives
Monoclonal antibodies (e.g., anti-IL17)	5 half lives

During washout, subjects may continue taking usual care of visible skin (face and scalp) for cosmetic reasons and of extremities (hands and feet) to avoid functional consequences on walking or moving their fingers. Subjects may shower, but not bathe or swim. The IGA will be evaluated on the rest of the body at Baseline.

After completing any necessary washout of prohibited medications, subjects will return to the site to complete the study eligibility requirements.

9.8.1 Permitted Therapies

Subjects will be advised on permitted emollient(s) for use as often as needed on nontreatment days during the study; on treatment days, the use of emollient(s) is permitted except within 4 hours before or after study drug application. Similarly, protective sunscreen should be applied as often as needed, except within 4 hours before or after study drug application. Subjects may use their standard of care treatment on their faces and/or palms/soles after the Week 4 assessment if they experience a worsening of IGA in those areas. In the US/EU, this may include compounded emollients with keratolytics (alpha or beta hydroxyl acids) and/or urea. These standard of care treatments should be approved by the investigator and documented in the eCRF.

Subjects who enter the OLE must stop standard of care treatment. If they experience a worsening of IGA they may use standard of care treatment on their faces and/or palms/soles after the Week 16

visit if the standard of care does not contain prohibited medications. If those standard of care treatments include prohibited medications, the subject should be discontinued from the study.

Other concomitant medications are allowed (e.g., analgesics, antihistamines), but should be limited to those medications considered necessary. All concomitant medications, both prescribed and over-the-counter, should be recorded in the eCRF.

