13.1.4.1 Efficacy Endpoints

Primary efficacy endpoint: The proportion of subjects in each treatment group who experience successful resolution of LI where “success” is defined as clear/almost clear overall and at least a 2-grade change from Baseline at Day 90/EOT in the Double-blind Period on the 5-point IGA scale.

Secondary: The secondary endpoints are as follow:

- The difference in mean scores between the active trifarotene cream HE1 and vehicle groups in the following assessment indices from Baseline through Day 90:
 - 5-point VIIS scale for scaling
 - Individual score for roughness (Scale: 0–4)
 - Palm/sole Assessment (Scale: 0–4)
 - Quality of life per DLQI and cDLQI
- The difference in proportion of subjects with presence of fissures on palm/soles (presence/absence, number of fissures, and pain associated with fissures [on a 0-3 scale]) at Day 90 between the active trifarotene cream HE1 and vehicle groups

Exploratory: The exploratory endpoints are as follow:

- The difference in mean ectropion scores (ESS of 0–8) between the active trifarotene cream HE1 and vehicle groups from Baseline through Day 90
- The difference in quality of life per EQ-5D-5L and EQ-5D-Y scores between the active trifarotene cream HE1 and vehicle groups from Baseline through Day 90

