9.8.2 Prohibited Therapies

The medications listed in [Table 9-1](#) are prohibited during the study. Balneotherapy is also prohibited during the Screening Period and during the study.

Subjects may not use concomitant keratolytics such as urea, salicylic acid, alpha, or beta hydroxyacids. Subjects may not use topical or systemic retinoids. Subjects may not take more than 3500 IU/day Vitamin A (e.g., as in a multivitamin). Use of benzoyl peroxide is permitted on nontreatment days for subjects with concomitant acne only); it must not be applied on treatment days due to risk of inactivation of trifarotene by benzoyl peroxide.

Subjects receiving excluded therapies will be ineligible for study enrollment or for continued treatment in the study, at the investigator's discretion with consultation with Mayne Pharma LLC and the medical monitor. For enrolled subjects who require prescription of a systemic azole, the principal investigator should discuss with the medical monitor whether the subject may continue in the study.

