10.3.1.1 Investigator's Global Assessment

The primary endpoint is the number of subjects in each treatment group who experience successful resolution of LI where “success” is defined as clear/almost clear and at least a 2-grade change from Baseline at Week 12/EOT in the Double-blind Period on a 5-point IGA full body scale.

The investigator will rate the subject's condition using the 5-point IGA at each time point shown in the Schedule of Events (Section 2.2).

The IGA will be measured on a 5-point scale, excluding the following areas: knees, elbows, neck, palms, soles, axillae, groin, and scalp:

0	Clear	No scaling and no roughness
1	Almost Clear	Occasional fine scales; hardly palpable roughness (mostly smooth)
2	Mild	Small and fine scales predominate; no more than a few large scales; mild roughness on palpation
3	Moderate	Some large scales that may be thick; coarse roughness on palpation
4	Severe	Confluent, primarily large (>1 cm), thick scales with plate-like hyperkeratosis

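### Keratolytic standard of care on face, palms and soles after Week 4 is both permitted and prohibited, and its IGA trigger cannot be scored on palms or soles

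*Protocol*

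**What the plan says.** The passages on treatment and on the IGA are in the Amendment 2 text of the Protocol.

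- **Permission (Section 9.8.1).** In the double-blind period, "Subjects may use their standard of care treatment on their faces and/or palms/soles after the Week 4 assessment" when the IGA has worsened on that skin. On content, for the US and EU, "this may include compounded emollients with keratolytics (alpha or beta hydroxyl acids) and/or urea". The investigator must approve the use and it goes into the eCRF.
- **Prohibition (Section 9.8.2).** "Subjects may not use concomitant keratolytics such as urea, salicylic acid, alpha, or beta hydroxyacids". The medications of Table 9-1 "are prohibited during the study. Balneotherapy is also prohibited during the Screening Period and during the study". Table 9-1 (Section 9.8) lists "Keratolytics (such as urea, lactic acid, propylene glycol, salicylic acid) except keratolytic shampoo", so shampoo is the only exception.
- **Consequence (Section 9.8.2).** "Subjects receiving excluded therapies will be ineligible for study enrollment or for continued treatment in the study, at the investigator's discretion", after consultation with the sponsor and the medical monitor.
- **Open-label extension (Section 9.8.1).** Standard of care is allowed only if free of prohibited medications; otherwise the subject is to leave the study. The double-blind paragraph carries no such condition.
- **Trigger scale (Section 10.3.1.1).** The IGA is scored "excluding the following areas: knees, elbows, neck, palms, soles, axillae, groin, and scalp".
- **Endpoints (Section 13.1.4.1).** The secondary endpoints include the mean palm/sole score (0–4) and "The difference in proportion of subjects with presence of fissures on palm/soles".

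**The concern.** A site whose subject has worsening palms after Week 4 finds two opposite instructions in adjacent subsections. Under one, a urea or hydroxy-acid product is allowed with approval. Under the other it is an excluded therapy that can end study treatment. Two sites could treat the same situation differently, and both could cite the protocol.

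The condition for use does not resolve this. It refers to a change in a score that is not taken on palms or soles, so access there rests on a judgement for which the protocol provides no scale.

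Two things are at stake in the analysis. A user's per-protocol status depends on which subsection is read. And two secondary endpoints are scored on exactly the skin that may receive an active non-study treatment between the Week 4 visit and the Day 60 and Day 90 visits.

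**Working it through.** **Passages side by side**

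| Question | Section 9.8.1, double-blind | Section 9.8.2 and Table 9-1 |
|---|---|---|
| Urea on palms/soles after Week 4? | Allowed, with approval | Prohibited |
| Alpha or beta hydroxy acids there? | Allowed, with approval | Prohibited |
| Exception or cross-reference to the other rule? | None | None; only shampoo is excepted |
| Status of a user | Compliant | May be ineligible for continued treatment |

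Section 10.3.1.1 leaves palms and soles out of the IGA. Section 9.8 adds that the Baseline IGA is taken on the body apart from face, scalp, hands and feet. There is thus no IGA value on palms or soles from which worsening could be measured. A palm/sole score and a fissure assessment are recorded at every clinic visit, but the trigger does not refer to them.

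For the per-protocol set, Section 13.1.1 requires that there be no significant deviations. Section 13.1.2.2 exempts tapering and drug holidays by name and does not mention this use.

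**Possible size**

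The protocol gives no effect size or power for the palm/sole or fissure endpoints, so there is no figure of its own to reproduce. Only the 32 evaluable subjects per arm (Section 13.2) and the two-sided 0.05 level (Section 13.1) come from the document. Everything else below is assumed.

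*Palm/sole mean.* Assume a true difference of 0.8, SD 1.0, use by a share v on vehicle and a on active, and a gain of g grades in users:

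difference = 0.8 − g(v − a); power ≈ Φ(difference × √(32/2) / 1.0 − 1.96)

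| v / a | g = 0.5 | g = 1.0 |
|---|---|---|
| 0 / 0 | 0.80, power 89% | 0.80, power 89% |
| 20% / 10% | 0.75, 85% | 0.70, 80% |
| 40% / 20% | 0.70, 80% | 0.60, 67% |
| 20% / 20% | 0.80, 89% | 0.80, 89% |
| 10% / 20% | 0.85, 93% | 0.90, 95% |

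*Fissures at Day 90.* Assume 60% on vehicle and 30% on active without standard of care, with v and a now the shares of fissured subjects who use it, and clearance in a share c of users:

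difference = 0.60(1 − vc) − 0.30(1 − ac); power by the pooled normal approximation at 32 per arm

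| v / a | c = 0.25 | c = 0.50 |
|---|---|---|
| 0 / 0 | 30.0 points, power 68% | 30.0 points, 68% |
| 20% / 10% | 27.7, 62% | 25.5, 55% |
| 40% / 20% | 25.5, 55% | 21.0, 41% |
| 20% / 20% | 28.5, 64% | 27.0, 60% |
| 10% / 20% | 30.0, 69% | 30.0, 69% |

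A loss on the palm/sole mean needs higher use on vehicle. With equal use the mean difference does not move and the fissure difference shrinks a little. With more use on active, the mean difference grows.

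**The case against.** The conflict may be only a missing cross-reference. The summary of changes for Amendment 2 shows that the permission was added on purpose, so that worsening subjects could return to approved standard of care. The open-label paragraph bars prohibited medications and the double-blind paragraph does not, which fits an intended exception. That is a fair reading of intent, but it does not settle the text: Section 9.8.2 was edited in the same amendment and its keratolytic sentence was left without an exception. It also does nothing for the trigger.

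A reader might go further and infer that values after such use enter the Day 90 comparisons unchanged and dilute them. The documents do not support this.

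- Section 13.1.4.3 names the terms of the repeated-measures model and is silent on values after standard-of-care use. Such handling is commonly left to the statistical analysis plan, which is not shown.
- Greater use on vehicle is plausible, since use follows worsening, but it is not established. Section 5.3 lists scaling and dryness among reactions to the drug itself, so active subjects may also come to worsen.

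A reader might also want one analysis rule fixed now, such as counting every user as fissured or setting later scores to missing. That is a choice of estimand. The first rule would label as fissured a subject treated only for thickening and, if vehicle use were higher, would inflate the drug effect.

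The per-protocol question is partly deferred, to decisions before database lock and to a deviation guidance plan. Those decisions still need a protocol that says whether the use is allowed. Finally, these are secondary endpoints for which the trial was not sized, so the stakes are moderate.

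**Conclusion.** The contradiction and the unusable trigger stand on the text alone and rest on no assumption. As written, the same use is compliant under Section 9.8.1 and, under Section 9.8.2, possible grounds for ending treatment and for a per-protocol exclusion.

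The effect on the palm/sole and fissure comparisons is conditional. With 40% use on vehicle and 20% on active, the assumed mean difference of 0.8 falls to 0.7–0.6 and the assumed 30-point fissure difference to 25.5–21.0 points. With equal use the mean difference stays at 0.8. No usage rate or treatment effect in the documents says which case applies, and the protocol does not state how values after such use are handled.

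One limit applies. The document also contains what appears to be later text, with Day 90 wording and COVID-19 provisions, but it begins at Section 13. Its Section 9 is not shown, so whether the conflict was resolved there cannot be checked.

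**What to change.** 1. Reconcile Sections 9.8.1 and 9.8.2 and Table 9-1 so that they give one answer for the double-blind period. Which clinical rule applies is for the sponsor to decide.
2. Tie the trigger to a score that is actually recorded on the area concerned.
3. State whether such use is a significant deviation for the per-protocol set, as Section 13.1.2.2 already does for tapering and drug holidays.
4. Have the eCRF record the area and start date of use. Section 9.8.1 asks for documentation but names neither.
5. Add a sensitivity analysis of the palm/sole and fissure endpoints that accounts for this use, with the estimand left to the sponsor.

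The cost is amendment wording, two eCRF fields and one additional analysis for each endpoint. If Section 9 of the later text already reconciles the passages, items 1 and 2 may need no change.
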